8.2.3.3. Proportion of School and/or Work Attendance Days

The proportion of school and/or work attendance days will be modeled via analysis of variance (ANOVA). The model will include fixed effect terms of treatment group and the randomization stratification factor HU use, age and geographic region. The proportion of subjects who were absent from school/and/or work, the frequency distribution of days absent from school and/or work, and the exposure adjusted incidence of absence from school and/or work will be tabulated by treatment group.

8.3. Safety

Safety analysis will be performed on all subjects as well as adolescents receiving at least one dose of study drug, with Groups 1 and 2 combined. All safety assessments, including AEs, clinical laboratory evaluations, vital signs, physical examinations, 12-lead ECG results, and echocardiograms will be summarized with descriptive statistics.

8.3.1. Summary of Exposure

Study drug administration will be summarized with number and percentage of subjects receiving from 1 to the maximum number of doses by treatment group. Similarly, the duration of treatment will be summarized with descriptive statistics.

8.3.2. Concomitant Medications

Concomitant medications will be coded using the WHO Drug Dictionary (version WHO-DD 01Sep2016). Concomitant medications will be summarized descriptively by treatment group.

8.3.3. Adverse Events

AEs will be mapped to system organ class (SOC) and preferred term using the Medical Dictionary for Regulatory Activities (MedDRA) version 19.1.

The total number and percentage of subjects with TEAEs will be presented by SOC and preferred term for each treatment group. TEAEs will be presented by severity. TEAEs will be tabulated presenting the SOC alphabetically and within each system the preferred term will be presented in decreasing order of the total number of voxelotor-treated subjects who experienced each TEAE. Treatment-related adverse events will be similarly presented.

The frequency of subjects who experience each TEAE or treatment-related AE will be determined as follows: A subject experiencing the same AE multiple times will only be counted once for the preferred term. Similarly, if a subject experiences multiple AEs within the same SOC, that subject will be counted only once for that system. If changes in the severity of an AE are recorded in the eCRF, only the most severe incidence of the AE will be counted. If a subject experiences multiple occurrences of a TEAE, only the related event or the worst severity

(analysis dependent), will be counted for each subject within each SOC or preferred term for the summaries of treatment-related AEs.

Missing onset dates will be imputed as previously outlined in [Section 6.3.6](#) as required to determine treatment-emergent events. Should an event have a missing severity or relationship to study medication, then the severity or relationship, respectively, will be classified as missing for summary tabulation purposes.

Listings of AEs leading to discontinuation of the study, SAEs and deaths, if any, will be provided.

Annualized incidence rates of VOC, ACS and pneumonia, priapism, and osteonecrosis will be summarized by treatment group and severity grade.

8.3.4. Clinical Laboratory Assessments

All hematology and chemistry laboratory assessments were performed by a central laboratory. Laboratory data will be converted into System International (SI) units for the analysis.

The following protocol-specified clinical laboratory findings will be summarized using descriptive statistics by treatment group, without any imputation:

1. Hematology:
 - a. Hemoglobin
 - b. Neutrophils
 - c. Platelets
 - d. Absolute reticulocytes
 - e. Reticulocyte %
 - f. WBC
2. Chemistry:
 - a. Alkaline phosphatase
 - b. ALT
 - c. AST
 - d. Indirect bilirubin
 - e. Potassium

Descriptive statistics will be presented for baseline, each evaluation post baseline, and change from baseline for each post baseline evaluation. If any of the clinical laboratory assessments are below the lower limit of quantitation or above the upper limit of quantitation, then the numerical limit will be used in the tabulation of the descriptive statistics.

Laboratory abnormalities will be graded via the Common Terminology Criteria for Adverse Event (CTCAE) version 4.0. The number and percentage of subjects experiencing treatment-emergent graded abnormalities will be summarized by treatment group. Laboratory abnormality shifts from baseline through Week 24 will be summarized by treatment group. Laboratory abnormality shifts of an increase of one grade or more from baseline will be presented in a data listing.

8.3.5. Vital Signs

Vital signs (oral temperature, respiratory rate, heart rate, and systolic/diastolic blood pressure) will be summarized using descriptive statistics for baseline, each study evaluation, and change from baseline for each post-baseline evaluation.

The average of each vital sign parameter collected at Screening and Day 1 (pre-dose) will be the baseline.

8.3.6. 12-lead Electrocardiograms

Twelve-lead electrocardiogram data (ventricular heart rate [HR] and conduction intervals [RR, PR, QRS, QT, and QTcF]) will be reported for subjects with clinically significant findings. These clinically significant ECG findings will be presented in listings.

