1.4. Safety Objectives

The safety objectives are to assess the safety of voxelotor compared to placebo based on AEs, clinical laboratory tests, physical examinations, and other clinical measures (eg, discontinuations due to AEs, dose reductions).

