4.4.2. Electrocardiograms

Electrocardiograms (ECGs) (12-lead) will be recorded after a participant has rested for at least 5 minutes in the supine position. At the visits that an ECG is conducted, a single 12-lead ECG will be conducted.

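### SAP 8.3 promises descriptive summaries of 12-lead ECG results, but SAP 8.3.6 provides only listings of subjects with clinically significant findings; the two need reconciling, with by-arm tables of PR, QRS and QTcF

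*SAP*

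**What the plan says.** SAP 8.3 (Safety) sets a general rule: "All safety assessments, including AEs, clinical laboratory evaluations, vital signs, physical examinations, 12-lead ECG results, and echocardiograms will be summarized with descriptive statistics".

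SAP 8.3.6 (12-lead Electrocardiograms) is narrower. Heart rate and the RR, PR, QRS, QT and QTcF intervals "will be reported for subjects with clinically significant findings. These clinically significant ECG findings will be presented in listings". It names no table, baseline, visit or treatment-group summary, and does not say what makes a finding clinically significant or who decides.

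The neighbouring sections are fuller. SAP 8.3.5 says that vital signs "will be summarized using descriptive statistics for baseline, each study evaluation, and change from baseline for each post-baseline evaluation". SAP 8.3.4 gives laboratory values the same three summaries by treatment group, plus counts and percentages of graded abnormalities.

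On collection, Protocol 4.4.2 says "At the visits that an ECG is conducted, a single 12-lead ECG will be conducted". The schedule of assessments (Protocol Appendix A) marks ECGs at Screening, Day 1, Weeks 4, 8, 12, 16, 20 and 24, and at later visits, with no difference by arm. Column alignment at the right-hand end of the extracted table is uncertain.

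**The concern.** A programmer given 8.3 would build ECG tables; one given 8.3.6 would build a listing. Usual practice is to follow the specific section over the general one, and here that leaves only the listing.

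A listing restricted to ECGs already called significant describes individuals. It does not give the mean change in an arm, the spread, or the number of subjects with an evaluable ECG at each visit. A modest dose-related lengthening of PR, QRS or QTcF, with few individual tracings remarkable, could therefore go unseen, although two doses and a concurrent placebo arm would allow it to be examined. The SAP gives no reason for treating ECG intervals differently from laboratory values and vital signs.

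Prespecification is also at stake. Under SAP section 10, analyses reported but not mentioned in the SAP must be identified as additional. If 8.3.6 is taken as the plan, a by-arm ECG table produced later would fall in that class.

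**Working it through.** The plan states no ECG figure to reproduce, so the first check is of the text and the second sizes what a by-arm summary could show.

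**1. The texts side by side**

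| Source | Subjects covered | Output |
|---|---|---|
| SAP 8.3 | All treated subjects (and adolescents), Groups 1 and 2 combined | Descriptive statistics |
| SAP 8.3.6 | Subjects with clinically significant findings | Listing |
| SAP 8.3.4 (laboratory) | By treatment group | Baseline, each evaluation, change; graded counts |
| SAP 8.3.5 (vital signs) | No selection stated | Baseline, each evaluation, change |
| Protocol 8.4.6 | Treated participants | Names BP, HR and laboratory data; not ECG |

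The first two rows differ in both subjects and output. Protocol 8.4.6 does not settle which governs. The sentence in 8.3 also names echocardiograms, which are not in the schedule of assessments, so it reads as a general statement not checked against the detailed sections.

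**2. Precision of a by-arm comparison, if one were tabulated**

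Inputs:
- 274 randomized subjects (SAP 6.1), allocated 1:1:1 (SAP 2.1): 274 / 3 = 91.3, so about 91 per arm.
- SD of QTcF change from baseline: not in the documents. Assumed 10 to 25 ms.
- 60 evaluable per arm at a visit: assumed, to show the effect of missing ECGs.

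Formula: half-width = t(0.975, 2n − 2) × SD × √(2/n), for one dose against placebo at one visit. The t quantile is 1.973 for n = 91 and 1.980 for n = 60.

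Example, n = 91 and SD 20: SE = 20 × √(2/91) = 2.96 ms; half-width = 1.973 × 2.96 = 5.85 ms (computed unrounded).

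| Assumed SD (ms) | Half-width, n = 91 (ms) | Half-width, n = 60 (ms) | Power for a 10 ms difference, n = 91 | Power, n = 60 |
|---|---|---|---|---|
| 10 | 2.93 | 3.62 | >99% | >99% |
| 15 | 4.39 | 5.42 | 99% | 96% |
| 20 | 5.85 | 7.23 | 92% | 78% |
| 25 | 7.31 | 9.04 | 77% | 59% |

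Power is two-sided at 5%.

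**3. Why a selected listing is a poor substitute**

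Assume normal changes with SD 20 ms and 91 subjects at one visit. The expected number beyond a cut is 91 × [1 − Φ((cut − shift)/SD)]. The cuts are illustrative only.
- Cut of 60 ms: 0.12 subjects with no shift, 0.57 with a 10 ms mean shift.
- Cut of 30 ms: 6.08 with no shift, 14.44 with a 10 ms mean shift.

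What a listing reveals thus depends on the criterion for entering it, which the visible SAP does not define. With a strict criterion, a 10 ms mean shift leaves almost no trace.

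**The case against.** The best case for the plan is that this is a small wording mismatch. Several parts of that case stand.

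- The contents page shows table titles in SAP section 13.1, but they are not visible in the public copy, and withheld text is not an omission. A reader might infer that the plan contains no by-arm ECG summary at all. The documents do not support that; the point covers only the visible methods text, which conflicts whatever the table list holds.
- Protocol 1.4 aims to "assess the safety of voxelotor compared to placebo", which might suggest that a placebo-controlled QTcF estimate was a stated objective now being discarded. It was not: that sentence goes on to name adverse events, laboratory tests, physical examinations and other clinical measures, and neither it nor the synopsis safety endpoint names ECG. The tracings are also still collected.
- Selection for the listing might be taken to rest on investigator judgement. SAP 8.3.6 does not say who judges.
- The documents do not state that intervals are captured for every ECG. The schedule and the interval list in 8.3.6 imply it.
- Some safeguards exist. Heart rate is already summarized as a vital sign, ECG-related adverse events would appear in the by-arm TEAE tables, and listings are sorted by treatment group, so flagged subjects can be counted against known arm sizes.
- Confidence intervals for differences would exceed what the SAP gives laboratory values or vital signs.

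These points narrow the concern to PR, QRS and QTcF and make a formal comparison optional. They do not remove the conflict between two current sections, and none of the safeguards shows a mean change in an interval.

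**Conclusion.** The inconsistency is real: SAP 8.3 and 8.3.6 cannot both be followed. If 8.3.6 governs, the visible methods give no by-arm summary of PR, QRS or QTcF from ECGs scheduled repeatedly in all three arms. This does not touch the primary efficacy analysis, but it is worth correcting.

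The potential precision is useful but conditional: a half-width of about 3 to 7 ms with about 91 per arm, and about 4 to 9 ms with 60, for an assumed SD of 10 to 25 ms. A reader might infer that the trial could reliably detect or exclude a 10 ms QTcF effect. That is too firm. Power for 10 ms falls to 77% at SD 25 with 91 per arm and 59% with 60. The ECGs are also single recordings, with no timing relative to dosing stated in the visible text after Day 1. Any comparison is supportive evidence, not a dedicated QT assessment.

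**What to change.** Rewrite SAP 8.3.6 so that it carries out 8.3:

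1. Tabulate PR, QRS and QTcF, and ECG heart rate, as recorded, by treatment group, at baseline, at each visit and as change from baseline. Use the baseline in SAP section 4 (average of pre-treatment values) and the windows in SAP Table 1; neither needs new definitions. State the number evaluable in each cell.
2. Add the number and percentage per arm exceeding QTcF limits, absolute and change from baseline, written into the SAP before Group 2b is unblinded.
3. Keep the listing of clinically significant ECGs as a supplement, and state the criterion and who applies it.
4. Optionally, give voxelotor-minus-placebo differences with 95% CIs for QTcF, labelled supportive.
5. If the unseen table list already contains ECG tables, align the text of 8.3.6 with them.

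The cost is a paragraph of SAP text and a few tables, with no extra ECGs. That holds provided intervals are in the database for all scheduled ECGs, which should be confirmed first. If they are not, the SAP should say so and 8.3 should be amended to match what can be reported.

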9. PROTOCOL DEVIATIONS

Protocol deviations as assessed by the study team will be displayed in a data listing and sorted by treatment group, subject number, and then by date (where applicable) within each subject number. The type of deviation along with a description and any additional comments about the deviation will be listed.

10. CHANGES IN THE PLANNED ANALYSES

Additional analyses that are included in the clinical study report but are not mentioned in the SAP will be identified as such.

11. PROGRAMMING CONVENTIONS

- Page orientation, margins, and fonts: Summary tables, listings, and figures will appear in landscape orientation. There should be a minimum of a 1.25” boundary on the upper (bound) edge, and a minimum of a 1.0” boundary on the remaining three edges. Output should be printed in Courier New with a point size of 8. Titles may be printed using a larger font (e.g., Arial point size 10).
- Identification of analysis population: Every summary table and figure should clearly specify the analysis population being summarized. Listings will be prepared for all subjects.
- Group headers: In the summary tables, the group headers will identify the summary group and the sample size for the indicated analysis population. Of note, the header’s sample size does not necessarily equal the number of subjects actually summarized within any given summary module; some subjects in the analysis population may have missing values and thus may not be summarized.
- Suppression of percentages corresponding to null categories: When count data are presented as category frequencies and corresponding percentages, the percent should be suppressed when the count is zero in order to draw attention to the non-zero counts.
- Presentation of sample sizes: Summary modules should indicate, in one way or another, the number of subjects actually contributing to the summary statistics presented in any given summary module. As mentioned above, this may be less than the number of subjects in the analysis population due to missing data.
 - In the quantitative modules describing continuous variables (and thus presenting sample size, means, and standard deviations), the sample size should be the number of non-missing observations. The number of missing observations, if any, will be noted.
 - For categorical variables that are presented in frequency tables, the module should present the total count in addition to the count in each category. Percentages should be calculated using this total as the denominator, and the percentage corresponding to the sum itself (that is, 100%) should be presented so as to indicate clearly to a reviewer the method of calculation. The number of missing observations, if any, will be noted.
- Sorting: Listings will be sorted by treatment group, subject number, and (where applicable) then by date within each subject number. If a listing is sorted in a different manner, a footnote will indicate as such.
- General formatting rules: Rounding for all variables will occur only as the last step, immediately prior to presentation in listings, tables, and figures. No intermediate rounding will be performed on derived variables. The standard rounding practice of

rounding numbers ending in 0-4 down and numbers ending in 5-9 up will be employed.

- The presentation of numerical values will adhere to the following guidelines:
 - Raw measurements will be reported to the number of significant digits as captured electronically or on the CRFs.
 - Standard deviations will be reported to one decimal place beyond the number of decimal places the original parameter is presented.
 - Means will be reported to the same number of significant digits as the parameter.
 - Calculated percentages will be reported with no decimals.
- Dates will be formatted as DDMMMYYYY. Partial dates will be presented on data listings as recorded on CRFs.
 - Time will be presented according to the 24-hour clock (HH:MM).

[REDACTED]	[REDACTED]
[REDACTED]	[REDACTED]
[REDACTED]	[REDACTED]
[REDACTED]	[REDACTED]
[REDACTED]	[REDACTED]
[REDACTED]	[REDACTED]
[REDACTED]	[REDACTED]
[REDACTED]	[REDACTED]
[REDACTED]	[REDACTED]
[REDACTED]	[REDACTED]
[REDACTED]	[REDACTED]
[REDACTED]	[REDACTED]
[REDACTED]	[REDACTED]
[REDACTED]	[REDACTED]

[REDACTED]

[REDACTED]	[REDACTED]
[REDACTED]	[REDACTED]
[REDACTED]	[REDACTED]
[REDACTED]	[REDACTED]
[REDACTED]	[REDACTED]
[REDACTED]	[REDACTED]
